Non-Elective: The procedure could not be deferred without increased risk of compromised cardiac outcome; includes Urgent and Emergent:

- **Urgent** – Procedure required during same hospitalization in order to minimize chance of further clinical deterioration.
- **Emergent** – An emergency operation is one in which there should be no delay in providing operative intervention.

Renal Complications*(Sponsor Definition)*

Renal Complication is defined as new need for replacement therapy, including hemodialysis, renal transplant, continuous renal replacement therapy, peritoneal dialysis, etc.

Severe Bleeding*(Sponsor Definition)*

Severe bleeding is a fatal, life-threatening, extensive, or major bleeding, as defined by MVARC.

SF-36v2

A survey with 36 questions that results in two scales of mental and physical functioning and overall health related quality of life.

SF-12v2: A 12 question abridged and validated version of the SF-36v2

Stroke/TIA (Transient Ischemic Attack)*(MVARC 2015 Definition)***Stroke Diagnostic Criteria:**

- I. Acute episode of a focal or global neurological deficit with at least one of the following:
 - A. Change in level of consciousness
 - B. Hemiplegia, hemiparesis, numbness, sensory loss affecting one side of the body
 - C. Dysphasia or aphasia, hemianopia, amaurosis fugax, other neurological signs or symptoms consistent with stroke
- II. No other readily identifiable non-stroke cause for the clinical presentation (e.g., brain tumor, trauma, infection, hypoglycemia, peripheral lesion, pharmacological influences) to be determined by or in conjunction with a neurologist.*

The neurological event type classification

- I. Stroke:

Duration of symptoms:

 - A focal or global neurological deficit \geq 24 hours or
 - A focal or global neurological deficit $<$ 24 hours if available neuroimaging indicates a new intracranial or subarachnoid hemorrhage (hemorrhagic stroke) or central nervous system infarction (ischemic stroke) or
 - The neurological deficit results in death

- II. TIA: duration of a focal or global neurological deficit < 24 hours and neuroimaging does not demonstrate a new hemorrhage or infarct

Confirmation of the diagnosis by at least one of the following:

- I. Neurologist or neurosurgical specialist, or
- II. Neuroimaging procedure (CT scan or brain MRI)
- III. Non-neurologist physician (if neurologist is not available)
- IV. Clinical presentation alone***

Stroke types will be adjudicated as:

- I. Ischemic: an acute symptomatic episode of focal cerebral, spinal, or retinal dysfunction caused by an infarction of the central nervous system tissue
- II. Hemorrhagic: an acute episode of focal or global cerebral or spinal dysfunction caused by intraparenchymal, intraventricular, or subarachnoid hemorrhage
- III. Undetermined: if there is insufficient information to allow categorization as ischemic or hemorrhagic

Stroke severity

It is recognized that an assessment of stroke is incomplete without an appropriate measurement of the disability resulting from the stroke, hence, mRS closest to 90 days post event** will be used to assess clinical disability.

- I. **Disabling:** mRS score of ≥ 2 at 90 days (or the last available clinical visit with evaluable data) AND an increase in ≥ 1 mRS category from an individual's pre-stroke baseline
- II. **Non-disabling:** mRS score of < 2 at 90 days (or the last available clinical visit with evaluable data) or doesn't result in an increase in ≥ 1 mRS category from pre-stroke baseline

TIA

Acute episode of a focal or global neurological deficit fulfilling the following criteria:

- I. Resulting in at least one of the following
 - Change in level of consciousness
 - Hemiplegia
 - Hemiparesis
 - Numbness
 - Sensory loss affecting one side of the body
 - Dysphasia or aphasia
 - Hemianopia
 - Amaurosis fugax
 - Other neurological signs or symptoms consistent with stroke
- II. Duration of deficit could be one of the following:
 - A focal or global neurological deficit < 24 hours
 - Any available neuroimaging does not demonstrate a new hemorrhage or infarct
- III. No other readily identifiable non-stroke cause for the clinical presentation (e.g., brain tumor, trauma, infection, hypoglycemia, peripheral lesion, pharmacological influences) to be determined by or in conjunction with a neurologist.*

Notes:

**Patients with non-focal global encephalopathy will not be reported as a stroke without unequivocal evidence based upon neuroimaging studies.*

***Evaluation of stroke between 30 and 90 days is acceptable if 90-day follow-up not available*

****If a stroke is reported without evidence of confirmation of the diagnosis by one of these methods, the event may still be considered a stroke on the basis of the clinical presentation alone.*

6-Minute Walk Test (6MWT)

[figure not shown]
A submaximal exercise test used to assess aerobic capacity and endurance that entails measurement of distance walked over a span of 6 minutes.

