8.15. Discharge Evaluation/Data Collection

The following study procedures/data collection will be performed at discharge or at 7 days post-procedure, whichever comes first (Table 11):

Table 11: Discharge / 7 Days Post-Procedure

General Information	
 Discharge date
Clinical Information	
 Targeted physical exam Clinical evaluation / prior or recent hospitalization Concomitant Medication including diuretic dose/s Safety Evaluation and AE/DD assessments Modified Rankin Scale* TTE 12-lead ECG Ambulatory cardiac monitoring**
Laboratory Measurements†	
 BNP or NT-proBNP Complete Blood Count (CBC; including platelets) Comprehensive metabolic panel (including Albumin, Bilirubin, ALP, ALT, AST, creatinine, BUN) Coagulation Panel (PT or PTT; INR for patients on vitamin-K antagonist) GGT Uric acid and eGFR Troponin or CK/CK-MB (according to site standard practice)
Sub-study only	
 eDiary collection (including KCCQ, EQ-5D-5L, SF-12, mood questionnaire, and symptom burden) will resume for 1 year after discharge. Starting post discharge, question(s) will be administered daily until the 12-month follow-up visit. Activity Monitoring will resume at discharge daily until the 12-month follow-up visit. The patient will be discharged wearing the activity monitoring device.

* For patients who experience a stroke during the study, mRS will be conducted closest to 90 days post event. It is recognized that an assessment of stroke is incomplete without an appropriate measurement of the disability resulting from the stroke, hence, mRS closest to 90 days post event will be used to assess clinical disability. Every effort should be made to have a neurologist or neurology fellow perform the neurological assessments, or alternatively, a trained research team member certified in stroke assessment. mRS can be obtained by a certified research team member via phone interview with the patient or caregiver member if the patient is unable to visit the research office.^{53,54}

** All study patients will be monitored by an ambulatory cardiac monitor for at least 2 weeks immediately following discharge (except those with pre-existing or newly implanted functional PPM, ICD, CRT devices, or implantable cardiac monitor with real-time monitoring service).

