- The peak CK-MB measured within 48 h of the procedure rises to $\geq 10x$ the local laboratory ULN (Upper Limit of Normal) PLUS new ST-segment elevation or depression of ≥ 1 mm in ≥ 2 contiguous leads (measured 80 ms after the J-point)
- The peak CK-MB measured within 48 h of the procedure rises to $\geq 5x$ ULN with new pathological Q waves in ≥ 2 contiguous leads or new persistent (left bundle branch block) LBBB
- In the absence of CK-MB measurements and a normal baseline cTn, a cTn (I or T) level measured within 48 h of the PCI rises to $\geq 70x$ the local laboratory ULN PLUS new ST-segment elevation or depression of ≥ 1 mm in ≥ 2 contiguous leads (measured 80 ms after the J-point)
- The peak CK-MB measured within 48 h of the procedure rises to $\geq 35x$ ULN with new pathological Q waves in ≥ 2 contiguous leads or new persistent LBBB.

B. In patients with elevated baseline CK-MB (or cTn):

- The CK-MB (or cTn) rises by an absolute increment equal to those levels recommended above from the most recent pre-procedure level plus, new ECG changes as described.

II. Spontaneous MI (> 48 hours after index procedure):

Detection of rise and/or fall of cardiac biomarkers (preferably cTn) with at least 1 value above the 99th percentile URL (or ULN in the absence of URL) together with at least 1 of the following:

- A. Symptoms of ischemia
- B. ECG changes indicative of new ischemia (new ST-segment or T-wave changes or new LBBB) or new pathological Q waves in ≥ 2 contiguous leads
- C. Imaging evidence of a new loss of viable myocardium or new wall motion abnormality

III. MI associated with sudden, unexpected cardiac death‡:

Sudden cardiac death or cardiac arrest, often with symptoms suggestive of myocardial ischemia, and accompanied by presumably new ST-segment elevation or new LBBB and/or evidence of fresh thrombus by coronary angiography and/or at autopsy, but death occurs

before blood samples could be obtained or at a time before the appearance of cardiac biomarkers in the blood

IV. Pathological findings of an acute myocardial infarction‡

Note: The use of high sensitivity (hs)-troponins is recommended for diagnosis of Type II (spontaneous) MI, but has not been studied for assessment of periprocedural MI. Standard troponin assays are therefore recommended for evaluation of Type I MI

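### Periprocedural MI (Protocol Appendix A, I.A): the CK-MB ≥35x ULN criterion can add no case, and troponin-only patients with a normal baseline cannot qualify on new Q waves or LBBB alone

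*Protocol*

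**What the plan says.** Protocol Appendix A, Myocardial Infarction, part I.A covers events up to 48 hours after the index procedure in patients with a normal baseline biomarker. It gives four alternatives:

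1. Peak CK-MB "rises to $\geq 10x$ the local laboratory ULN (Upper Limit of Normal) PLUS new ST-segment elevation or depression" of at least 1 mm in two contiguous leads.
2. Peak CK-MB "rises to $\geq 5x$ ULN with new pathological Q waves" or new persistent left bundle branch block (LBBB).
3. "In the absence of CK-MB measurements and a normal baseline cTn, a cTn (I or T) level measured within 48 h of the PCI rises"; the threshold is 70x ULN, with the ST criterion of bullet 1.
4. Peak CK-MB again, which "rises to $\geq 35x$ ULN with new pathological Q waves" or new persistent LBBB.

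Part I.B covers an elevated baseline: "The CK-MB (or cTn) rises by an absolute increment equal to those levels recommended above", plus the ECG changes already described. Category II covers events after 48 hours. A footnote says that periprocedural elevations above ULN that miss these criteria are to be recorded as myonecrosis and not as MI.

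The protocol collects troponin and CK-MB as alternatives: at baseline (Section 8.8, Table 7), at 12-24 hours (Section 8.14.1, Table 10), at discharge or day 7 (Section 8.15, Table 11) and in the schedule of assessments (Section 8.21, Table 14). The Table 11 entry, worded the same way in Table 10, is "Troponin or CK/CK-MB (according to site standard practice". MI is a component of the 30-day MAE composite (Protocol 5.1; SAP 3.1) and so enters clinical success (Protocol 5.2.3; SAP 3.2).

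**The concern.** Bullets 2 and 4 name the same analyte, the same ECG findings and the same 48-hour window. They differ only in the threshold, and bullet 4 has the higher one. A higher threshold joined by an or to a lower one does nothing.

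The position of bullet 4 suggests what went wrong. CK-MB has an ST-segment criterion and a Q-wave/LBBB criterion. Troponin has an ST-segment criterion, and the slot where its Q-wave/LBBB criterion would stand names CK-MB instead.

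If so, the periprocedural definition lacks a troponin route that CK-MB has, in a study where a site may measure troponin only. An Appendix A note even recommends standard troponin assays for evaluating periprocedural MI. Two patients with the same new Q waves could then be classified differently, one as MI and one as myonecrosis, because their hospitals run different assays. That difference would pass into the MI component, the MAE composite and clinical success.

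**Working it through.** The plan states no figure for this point, so there is none to reproduce. The check is one of logic.

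**Step 1: is bullet 4 redundant?** CK-MB ≥35x implies CK-MB ≥5x, and the ECG findings and window are the same. Every case meeting bullet 4 therefore meets bullet 2.

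As a check, the four bullets were coded as rules and run over a grid:
- CK-MB absent or 0 to 100x ULN in whole steps (102 values)
- troponin absent or 0 to 100x ULN (102 values)
- ST shift yes/no
- Q waves or LBBB yes/no

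This gives 102 × 102 × 2 × 2 = 41,616 combinations. Bullet 4 as printed adds **0** beyond bullets 1 to 3.

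**Step 2: which analyte fits?**

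| | ST shift | Q waves/LBBB | ratio |
|---|---|---|---|
| CK-MB | 10x | 5x | 10/5 = 2 |
| Bullets 3 and 4 | 70x | 35x | 70/35 = 2 |
| ratio | 70/10 = 7 | 35/5 = 7 | |

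Both ratios match if bullet 4 is the troponin criterion. Nor can bullet 4 as printed take over bullet 3's opening condition, "In the absence of CK-MB measurements and a normal baseline cTn, a cTn (I or T) level", because it would then need a CK-MB value where none was measured.

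**Step 3: who is affected?** Take a normal baseline, an event within 48 h, troponin only, and new Q waves or LBBB. Troponin runs from 0 to 100x, giving 101 combinations per row.

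| | counted as printed | counted if bullet 4 is troponin ≥35x |
|---|---|---|
| no ST shift | 0 of 101 | 66 of 101 (35x to 100x) |
| with ST shift | 31 of 101 (70x to 100x, bullet 3) | 66 of 101 |

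The troponin reading adds 66 + (66 − 31) = 101 combinations. These are logical combinations, not expected patients, and the proportions say nothing about frequency. They locate the gap: Q waves or LBBB without ST shift at any troponin level, or with ST shift and troponin from 35x to below 70x.

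**Step 4: weight of one case.** With the planned maximum of 200 patients, one MI gained or lost moves a crude MAE proportion by 1/200 = 0.5 percentage points, provided that the patient has no other MAE within 30 days. The documents give neither an MI rate nor the share of troponin-only sites, so no total can be computed.

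**The case against.** The strongest reply is that the gap is narrow and may have no effect in practice.

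- **Other routes exist.** A reader might infer that troponin-only patients with new Q waves or LBBB cannot be counted as MI at all. The text does not support that. They qualify under bullet 3 if they also have ST shift and troponin ≥70x. Part I.B expressly admits troponin when the baseline is elevated. Category II, after 48 hours, asks for "Detection of rise and/or fall of cardiac biomarkers (preferably cTn" and accepts new LBBB or Q waves. Categories III and IV set no biomarker threshold. This limits the point but does not remove it: none of these routes serves a surviving patient with a normal baseline whose event falls within 48 hours, who has no qualifying ST shift and no pathological evidence.
- **The direction is not always downward.** A reader might also infer that the error carries into I.B and can only under-count. That is not shown. I.B refers back to the I.A levels, and I.A prints no Q-wave/LBBB level for troponin. Someone applying the 5x CK-MB level to troponin would count more cases than a 35x rule would. Under I.A the printed text can only count fewer than the troponin reading; under I.B the direction is open.
- **The working definition may differ.** The CEC applies definitions set in its Charter (Protocol 14.2), which is not among the documents and may already be right. Nor is the source from which the criteria were adapted. That troponin at 35x was meant is a strong inference from the list, not an established fact.
- **No decision rule depends on it.** SAP 2.3 says the sample size has no statistical justification, and no performance goal is stated for the MAE rate. The main analysis is Kaplan-Meier, so the 0.5 points is only a crude guide.

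The Appendix's advice to evaluate suspected MI carefully does not close the gap, because the footnote sends cases that miss the criteria to myonecrosis.

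**Conclusion.** The definition is wrong as written and should be corrected. It looks like a transcription error and not a deliberate choice. Bullet 4 of I.A adds no case whatever the data. Under I.A, a patient with a normal baseline and only troponin measured cannot qualify within 48 hours on new Q waves or LBBB unless ST shift and troponin ≥70x ULN are also present. The MI component therefore depends partly on the local assay, and clinical success with it.

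The redundancy and the gap follow from the printed text alone. The intended analyte and its 35x level rest on the list's internal pattern. The size is at most 0.5 points of the crude MAE rate per affected patient, assuming N=200 and MI as that patient's only MAE. The total is unknown and may be small. The documents do not show that any adjudicated case was misclassified.

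**What to change.** - Check bullet 4 of I.A against the cited source definition and the CEC Charter, and make all three agree. The likely result is a troponin criterion that applies when CK-MB was not measured and baseline troponin is normal, at 35x ULN with new Q waves or persistent LBBB.
- State in I.B which troponin increment goes with ST changes and which with Q waves or LBBB.
- In bullet 3, replace the reference to PCI with the study procedure. This is cosmetic, since the part I heading already ties the window to the index procedure.
- Re-check periprocedural events already adjudicated in patients with troponin only, including those recorded as myonecrosis.

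The cost is a wording change in Appendix A, and in the Charter if needed, plus a limited re-check. No new data collection or change of analysis method is required.

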Appendix B: Patient Preference Survey Template

[figure not shown]
Patient Preference Survey – Screening/Baseline

Page 1 of 4

[figure not shown]

Patient Preference Survey – Screening/Baseline

Patient Preference Survey – Screening/Baseline

[figure not shown]

Patient Preference Survey – Screening/Baseline

Appendix C: Katz Index of Independence in Activities of Daily Living

Katz Index of Independence in Activities of Daily Living

Appendix D: Instructions for 6-Minute Walk Test

[REDACTED]

[REDACTED]

[REDACTED]

[REDACTED]

[REDACTED]

[REDACTED]

[REDACTED]

[REDACTED]

Appendix E: Child-Pugh Score

[REDACTED]

[figure not shown]
[REDACTED]

Appendix F: Patient Edema Questionnaire Template

Edema Grading – Ankle Measurements – Patient Edema Questionnaire

[figure not shown]
Page 1 of 2

Note: Patient Edema Questionnaire on next page.

Edema Grading – Ankle Measurements – Patient Edema Questionnaire

Appendix G: Abbreviations

Below is a list of commonly used abbreviations in Transcatheter Tricuspid Clinical Studies

Abbreviation / Acronym	Definition
6MWT	6-Minute Walk Test
6MWD	6-Minute Walk Distance
ACC	American College of Cardiology
ACT	Activated Clotting Time
ADL	Activities of daily living
AE	Adverse Event
AF	Atrial Fibrillation
AHA	American Heart Association
AKI	Acute Kidney Injury
ALP	Alkaline phosphatase
ALT	Alanine transaminase
ASA	Acetylsalicylic acid
ASD	Atrial septal defect
AST	Aspartate aminotransferase
AT	As-Treated
BNP	B-type natriuretic peptide
BP	Blood pressure
BUN	Blood urea nitrogen
CABG	Coronary Artery Bypass Graft
CAVI	Caval valve implantation
CBC	Complete blood count
CE	Conformité Européenne
CEC	Clinical Events Committee
CFR	Code of Federal Regulations
CHF	Congestive Heart Failure
CI	Confidence interval
CIB	Clinical Investigator's Brochure
CIP	Clinical Investigational Plan
CK	Creatine kinase
CMP	Comprehensive metabolic panel
CMR	Cardiovascular Magnetic Resonance
COPD	Chronic obstructive pulmonary disease
CRF	Case Report Form
CRT	Cardiac resynchronization therapy
CSC	Clinical Screening Committee
CSHA	Canadian Study of Health and Aging (Clinical Frailty Scale)
CT	Computed Tomography

PROPRIETARY DATA: THIS DOCUMENT CONTAINS CONFIDENTIAL AND PROPRIETARY INFORMATION OF EDWARDS LIFESCIENCES, LLC. IT MUST NOT BE REPRODUCED OR DISCLOSED TO THIRD PARTIES WITHOUT PRIOR WRITTEN PERMISSION OF EDWARDS LIFESCIENCES, LLC.

Edwards Lifesciences, Edwards, the stylized E logo, and EVOQUE are trademarks of Edwards Lifesciences Corporation.

Abbreviation / Acronym	Definition
CTA	Clinical Trial Agreement
CV	Cardiovascular
CWD	Continuous Wave Doppler
DAPT	Dual anti-platelet therapy
DD	Device Deficiency
DOAC	Direct oral anticoagulant
DSMB	Data Safety Monitoring Board
DVT	Deep vein thrombosis
EACTS	European Association for Cardio-Thoracic Surgery
ECG	Electrocardiogram
eCRF	Electronic case report form
EDC	Electronic data capture
EF	Ejection Fraction
EFS	Early Feasibility Study
eGFR	Estimated glomerular filtration rate
EROA	Effective regurgitant orifice area
ESC	European Society of Cardiology
FDA	Food and Drug Administration
Fr	French
GCP	Good Clinical Practice
GLP	Good Laboratory Practice
GGT	Gamma-Glutamyl Transferase
GI	Gastrointestinal
HF	Heart Failure
Hgb	Hemoglobin
hx	History
ICD	Implantable cardioverter-defibrillator
ICF	Informed consent form
ICH	International Council for Harmonisation of Technical Requirements for Pharmaceuticals for Human Use
ICM	Implantable cardiac monitor
ICU	Intensive care unit
IFU	Instructions for Use
INR	International normalized ratio
IRB	Institutional Review Board
IVC	Inferior vena cava
ISO	International Standardization Organization
IVC	Inferior vena cava
KCCQ	Kansas City Cardiomyopathy Questionnaire
LAA	Left atrial appendage
LV	Left ventricle
LVEF	Left ventricular ejection fraction
MAE	Major Adverse Event

PROPRIETARY DATA: THIS DOCUMENT CONTAINS CONFIDENTIAL AND PROPRIETARY INFORMATION OF EDWARDS LIFESCIENCES, LLC. IT MUST NOT BE REPRODUCED OR DISCLOSED TO THIRD PARTIES WITHOUT PRIOR WRITTEN PERMISSION OF EDWARDS LIFESCIENCES, LLC. [REDACTED]

[REDACTED] Edwards Lifesciences, Edwards, the stylized E logo, and EVOQUE are trademarks of Edwards Lifesciences Corporation.

Abbreviation / Acronym	Definition
MAR	Medication administration record
MCOT	Mobile cardiac outpatient telemetry
MDR	Medical Device Regulation
MI	Myocardial Infarction
MR	Mitral Regurgitation
mRS	Modified Rankin Scale
MSAE	Major Serious Adverse Event
MSCT	Multi-slice computed tomography
MV	Mitral Valve
MVARC	Mitral Valve Academic Research Consortium
MVR	Mitral Valve Replacement
NSAIDs	Nonsteroidal anti-inflammatory drugs
NT-proBNP	N-terminal (NT)-pro hormone BNP
OAC	Oral anticoagulation
OMT	Medical Therapy
OR	Operating room
OUS	Outside the United States
NYHA	New York Heart Association
PA	Pulmonary Artery
PASP	Pulmonary Artery Systolic Pressure
PCW	Pulmonary capillary wedge
PE	Pulmonary embolism
PHTN	Pulmonary hypertension
PISA	Proximal Isovelocity Surface Area
PP	Per-protocol
PPM	Permanent pacemaker
PT	Prothrombin time
PTT	Partial thromboplastin time
PVL	Paravalvular Leak
PVR	Pulmonary vascular resistance
QOL	Quality of Life
RA	Right atrium
RV	Right ventricle
Rvol	Regurgitant volume
RVOT	Right ventricular outflow tract
SAE	Serious Adverse Event
SF-36	Short Form Health Survey
STS	Society of Thoracic Surgeons
SVT	Supraventricular tachycardia
TEE	Transesophageal echocardiography
TIA	Transient Ischemic Attack
TMVr	Transcatheter Mitral Valve Repair
TMVR	Transcatheter Mitral Valve Replacement

PROPRIETARY DATA: THIS DOCUMENT CONTAINS CONFIDENTIAL AND PROPRIETARY INFORMATION OF EDWARDS LIFESCIENCES, LLC. IT MUST NOT BE REPRODUCED OR DISCLOSED TO THIRD PARTIES WITHOUT PRIOR WRITTEN PERMISSION OF EDWARDS LIFESCIENCES, LLC. [REDACTED]

[REDACTED] Edwards Lifesciences, Edwards, the stylized E logo, and EVOQUE are trademarks of Edwards Lifesciences Corporation.

Abbreviation / Acronym	Definition
TR	Tricuspid Regurgitation
TTE	Transthoracic Echocardiography
TTVr	Transcatheter tricuspid valve repair
TTVR	Transcatheter tricuspid valve replacement
TV	Tricuspid valve
TVR	Tricuspid valve replacement
UADE	Unanticipated adverse device effect
US	United States
USADE	Unanticipated serious adverse device effect
VC	Vena contracta
VCA	Vena contracta area
VCW	Vena contracta width
VF	Ventricular fibrillation
VKA	Vitamin K antagonist
VT	Ventricular tachycardia
